11.2.8.3. Assessment of Adverse Events

11.2.8.3.1. Assessment of Severity

The Investigator will assess the severity of AEs according to the criteria below:

Mild: The AE did not cause interference with the subject's activity.

Moderate: The AE produced limited functional impairment and may have required therapeutic intervention. The AE produced no sequelae.

Severe: The AE resulted in significant impairment of function and may have lead to temporary inability to resume the subject's normal life pattern.

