6. INVESTIGATIONAL PLAN

6.1. Overall Study Design

This is a prospective, open label, single-arm, multi-center, Phase 2 study measuring the safety and tetanus antibody responses to Tdap vaccine administered to plasma donors every 3 months ± 1 week for 12 months (5 vaccinations) with a 6 month follow-up after the last vaccination. After obtaining informed consent and screening for eligibility including plasmapheresis donor eligibility, subjects will have other baseline assessments performed and if eligible, will receive the scheduled vaccinations, will be assessed for adverse events (AEs) and have plasma samples collected with antibody titers reported each month thereafter for 11 months, and then at 1 and 6 months after the last vaccination. Subjects will undergo plasmapheresis prior to the second through the fifth vaccination and at the 1 month and 6 month post vaccination follow-up visits. As these subjects are participating in a standard donor plasmapheresis donor program, assessments for donor eligibility and routine plasmapheresis will be performed; however, only the data specifically required to meet the objectives of this study will be collected. The study time and events schedule is shown in [Table 4](#). This table depicts those study specific procedures for which data will be collected and reported on an eCRF. In addition to these study specific assessments routine screening procedures to assure plasma donor suitability will also be performed. Some of the routine procedures performed as part of plasma donor screening evaluations such as vital signs, physical examinations, or laboratory tests will be reported as AEs (if appropriate) on an AE eCRF.

Table 4: Time and Events Schedule

Study Phase	Screening	Visits (Month 0 to Month 12 ± 1 week)												
Month	-7 to -1 days	0	1	2	3	4	5	6	7	8	9	10	11	12
Visit Number	1	2/3	4	5	6/7	8	9	10/11	12	13	14/15	16	17	18/19
Study Specific Procedures for which data are recorded on an eCRF														
Consent	X													
Eligibility checklist ^a	X	X			X			X			X			X
Demographics	X													
Medical history	X													
Medications	X	X			X			X			X			X
Vaccination		1			2			3			4			5
AEs	X	X	X	X	X	X	X	X	X	X	X	X	X	
Plasma sample for anti-tetanus and anti-diphtheria antibody titer ^b	X		X	X	X	X	X	X	X	X	X	X	X	
Urinalysis/ serum creatinine ^c		X			X			X			X			X
Diary card review ^d		X	X	X	X	X	X	X	X	X	X	X	X	
Procedures performed as part of routine plasma donor testing and pheresis														

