11.2.6. Urinalysis and Serum Creatinine

A dipstick urinalysis will be performed that tests for protein, blood, leukocyte esterase, nitrates, pH, specific gravity, ketones, bilirubin, and glucose. A blood sample will also be collected for a serum creatinine test. These tests will be performed to monitor for the possible development of immune complex-mediated glomerular disease.

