11.2.8. Adverse Events and Serious Adverse Events

11.2.8.1. Definitions

11.2.8.1.1. Adverse Event (AE)

An AE is defined as any treatment emergent unfavorable and unintended sign or symptom (including abnormal laboratory findings) that occur at any time after the subject has signed informed consent until the second follow up visit after the last study vaccination, whether or not considered drug related. These will be recorded as AEs in the eCRF.

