5.1. Safety Endpoints

Adverse Events: AEs will include any treatment emergent unfavorable and unintended sign or symptom including abnormal laboratory findings that occur at any time after the subject has signed informed consent until the second follow up visit after the last study vaccination, whether or not considered drug related.

Severity: All AEs will be assessed for severity by the investigator. Assignment of grade based on the intensity of symptoms and the degree of limitation of usual daily activities will be done according to severity using the following criteria:

Mild: The AE did not cause interference with the subject's activity.

Moderate: The AE produced limited functional impairment and may have required therapeutic intervention. The AE produced no sequelae.

Severe: The AE resulted in significant impairment of function and may have lead to temporary inability to resume the subject's normal life pattern.

Relationship: The degree of certainty for which the AE/SAE is attributed to the investigational product or alternative causes will be determined by the investigator's use of clinical judgment in conjunction with the assessment of a plausible biologic mechanism, a temporal relationship between the onset of the event in relation to receipt of the investigational product, and identification of possible alternate etiologies including underlying disease, concurrent illness or concomitant medications. Only a physician can make this determination.

The following drug relationships will be used for this clinical study:

Unrelated: There is no temporal relationship between the event and the administration of the product or the event is clearly due to the subject's medical condition, other therapies, or accident.

Unlikely: There is evidence of exposure to the product but there is another more likely cause of the event.

Possible: There is some temporal relationship between the event and the administration of the product and the event is unlikely to be explained by the subject's medical condition or other therapies.

Probable: The temporal relationship between the event and the administration of the product is compelling, and the subject's medical condition and other therapies cannot explain the event.

Definite: The event follows a reasonable temporal sequence from administration of the medication or follows a known or suspected response pattern to the medication.

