9.6. Clinical Laboratory Data

Laboratory data for urinalysis results and serum creatinine levels will be presented as summary statistics by visit as well as in by-subject data listings. The number and percentage of subjects with serum creatinine > 1.5 x upper limit of normal and urine indicative for proteinuria (2+) or hematuria (blood \geq 50 erythrocytes/ μ L).

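### The AE severity scale has no criterion for the size of a laboratory abnormality, so a symptom-free renal finding defaults to Mild whatever its value

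*Protocol*

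**What the plan says.** Protocol 11.2.8.1.1 defines an AE as "any treatment emergent unfavorable and unintended sign or symptom (including abnormal laboratory findings", and SAP 5.1 carries the same definition. Protocol 6.1 adds that findings from routine donor screening, namely "vital signs, physical examinations, or laboratory tests will be reported as AEs (if appropriate) on an AE eCRF", can also become AEs.

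The investigator grades AEs by three criteria in Protocol 11.2.8.3.1, repeated in SAP 5.1:

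- "Mild: The AE did not cause interference with the subject's activity"
- "Moderate: The AE produced limited functional impairment and may have required therapeutic intervention" (a further sentence says that there were no sequelae)
- "Severe: The AE resulted in significant impairment of function and may have lead to temporary inability to resume the subject's normal life pattern"

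SAP 5.1 states the basis of the scale: "Assignment of grade based on the intensity of symptoms and the degree of limitation of usual daily activities". The other scale, Protocol Table 5 (SAP Table B), covers only solicited diary events and has no creatinine or urinalysis row.

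On the renal tests, Protocol 11.2.6 says: "These tests will be performed to monitor for the possible development of immune complex-mediated glomerular disease". Protocol 12.2.3 summarizes the results over time. SAP 9.6 adds a count by size: "The number and percentage of subjects with serum creatinine > 1.5 x upper limit of normal and urine indicative for proteinuria (2"; it goes on to 2+ protein and to hematuria of at least 50 erythrocytes/µL. AE severity is part of the safety endpoint in Protocol 9.2.

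**The concern.** A laboratory finding reported as an AE must be given a severity grade, but the scale asks only how the event affected the subject. Early renal change is typically the kind of finding that a creatinine or dipstick test shows before the donor notices anything. For such findings the grade carries no information about how abnormal the value was.

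At stake is how the severity part of the safety endpoint is read. SAP Table 6 shows severity by vaccination number, which is where worsening over five closely spaced doses should become visible. If symptom-free protein rose from 1+ to 3+ across doses, the severity rows could stay at Mild throughout. A statement in the study report that there were no Moderate or Severe renal laboratory AEs could then reflect the scale and not the data.

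**Working it through.** The plan gives no figure to reproduce. The check is to hold a symptom-free finding against each criterion, and then to look for other places where its size is recorded.

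**Step 1: the criteria.** Mild has one condition, no interference with activity, and a symptom-free finding meets it. Moderate requires limited functional impairment. Treatment is joined to that by *and*, and is optional (*may have*), so treatment alone does not reach Moderate. The no-sequelae sentence restricts Moderate and gives no route up to it. Severe requires significant impairment of function. The SAP's basis, symptom intensity and limitation of daily activities, gives such a finding nothing on either count.

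**Step 2: illustrative values, no symptoms.** The values are chosen for illustration; 2+ in SAP 9.6 is read as 2+ or more.

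| Finding | Grade by the wording | Meets a SAP 9.6 threshold? |
|---|---|---|
| Creatinine 1.1 x ULN | Mild | No |
| Creatinine 3 x ULN | Mild | Yes (above 1.5 x ULN) |
| Protein 1+ | Mild | No |
| Protein 3+ | Mild | Yes |

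The SAP 9.6 thresholds separate the rows within each pair. The severity grade does not.

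**Step 3: comparison with the diary scale.** Protocol Table 5 grades redness by diameter and fever by temperature, with no activity condition. Redness above 10 cm is Grade 3 in a donor who feels well. The plan therefore already grades some measurable signs by size, but not laboratory values.

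**Step 4: where the size of a renal finding does appear.**

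| Place | What it shows |
|---|---|
| SAP Tables 6 and 10 | Mild/Moderate/Severe only; no laboratory size |
| SAP 9.6 | Three thresholds, but the sentence has no verb, and its *and*/*or* leaves open whether they are counted separately |
| SAP Table 12 shell | Dipstick protein and blood by category at Months 0, 3, 6, 9 and 12; creatinine only as Low or High |
| SAP Listing 9 | Each value, by subject |
| Protocol 11.2.8.1.5 | An important medical event can be serious whatever its severity grade |

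As the shells stand, creatinine above 1.5 x ULN is in no table, and its size can be read only from Listing 9.

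**Step 5: scale.** 100 subjects x 5 scheduled tests = at most 500 creatinine and 500 dipstick results. The documents do not say what share would be reported as AEs. If it were 1% to 5% of the 500 test occasions (an assumption with no source in the documents), that would be 500 x 0.01 = 5 to 500 x 0.05 = 25 AEs.

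**The case against.** The strongest reply is that the protocol separates severity from importance on purpose. Protocol 11.2.8.1.5 says that severe describes intensity and is not the same as serious. A symptom-free but dangerous creatinine rise can be an important medical event, reportable within 24 hours (11.2.8.4.1) and counted as an SAE in Table 6 and Listing 14. The size of an abnormality is a matter for laboratory tables, and SAP 9.6, Table 12 and Listing 9 provide them. This largely stands: the renal signal remains in the analysis. It does not repair the severity rows, because an important medical event can still be tabulated as Mild. The laboratory tables themselves lack the creatinine threshold.

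A reader might infer more than the documents support:

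- *That every such finding must be graded Mild, or that renal events cannot be Moderate or Severe.* The investigator assigns the grade, and neither document defines function. An investigator could read it as organ function, although the SAP's wording points to daily activities. Renal events with symptoms can be graded higher. Nor is the scale purely functional, since it mentions treatment, sequelae and symptom intensity; but none of these supplies a laboratory threshold.
- *That withdrawal for safety would be blocked.* Protocol 8.11 names a severe or serious AE only as an example. It separately lists risk to the subject and loss of donor eligibility, and section 10 has the medical monitor follow AE trends. No documented safety action depends on the severity grade alone.
- *That a value meeting a SAP 9.6 threshold should never be Mild.* Those thresholds are for tabulation, and nothing in the documents makes them a minimum severity grade.

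**Conclusion.** The gap is real and limited. Laboratory findings are AEs, the scale has no criterion for their size, and by its wording a symptom-free creatinine or urinalysis abnormality defaults to Mild. The severity rows of SAP Tables 6 and 10 would therefore not separate small from large findings of this kind. Only the severity component of the safety endpoint is affected, and only for symptom-free laboratory AEs; incidence and relationship are not.

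The conclusion rests on reading function as the subject's activity, as SAP 5.1 does. If investigators read it as organ function, some findings would be graded higher, but without a common rule, so grades could differ between assessors. The number of AEs affected is unknown: the 5 to 25 above depends wholly on the assumed rate. The point deserves correction before database lock because the recorded values allow it at little cost.

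**What to change.** SAP section 2 allows changes before the database is locked. Three edits are enough:

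1. In SAP 5.1, state that an AE which is a laboratory finding also receives a magnitude-based grade, derived from the recorded value on a published laboratory toxicity scale that the sponsor names. Show it beside the investigator's grade in Tables 6 and 10, without replacing that grade.
2. Complete the SAP 9.6 sentence. Say that the three thresholds are counted separately, and whether 2+ means 2+ or more.
3. Add the three thresholds (creatinine above 1.5 x ULN, proteinuria 2+, hematuria of at least 50 erythrocytes/µL) as rows in Table 12, by vaccination.

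SAP section 12, which now reports no changes from the protocol's analyses, should record the addition.

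The cost is a paragraph, a derived variable and a few table rows, all from data already collected. The downside is a little more programming, and some laboratory AEs may show as more than Mild on the derived grade.

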11.2.8.3.2. Assessment of Severity of Solicited Adverse Events by Subjects

The severity rating scale in [Table 5](#) will be provided to the subject to assess the severity of solicited AEs that are recorded in the diary. At the diary review, if any items are checked, a clinician will review these with the subject to confirm that the appropriate severity rating was selected. The subject will be provided with a small metric ruler with the diary to rate redness or swelling.

Table 5: Severity Rating Scale for Solicited Adverse Events to be Used with the Subject Diary

Adverse Event	Grade 0	Grade 1	Grade 2	Grade 3
Injection site redness	None	2.5 – 5 cm	5.1 – 10 cm	> 10 cm
Urticaria or other rash	None	No interference with activity	Some interference with activity	Significant; prevents daily activity
Injection site tenderness/ pain	None	No interference with activity	Some interference with activity	Significant; prevents daily activity
Injection site swelling	None	2.5 – 5 cm and does not interfere with activity	5.1 – 10 cm or interferes with activity	> 10 cm or prevents daily activity
Fever	None	100.4 – 101.1	101.2 – 102.0	102.1 – 104
Headache	None	No interference with activity	Repeated use of nonnarcotic pain reliever > 24 hours or some interference with activity	Significant; any use of narcotic pain reliever or prevents daily activity
Nausea/vomiting	None	No interference with activity or 1 – 2 episodes/24 hours	Some interference with activity or > 2 episodes/24 hours	Prevents daily activity, requires outpatient IV hydration
Chills, fatigue, joint pain malaise, muscle weakness (myalgia)	None	No interference with activity	Some interference with activity	Significant; prevents daily activity

11.2.8.3.3. Assessment of Causality

The investigator must make an assessment of relationship to the investigational product based on the following criteria:

Unrelated:	The subject did not receive the investigational product, the temporal sequence of the AE/SAE onset relative to administration of the investigational product is not reasonable, or there is another obvious cause of the AE/SAE.
Unlikely:	There is evidence of exposure to the investigational product but there is another more likely cause of the AE/SAE.
Possible:	There is evidence of exposure to the investigational product, the temporal sequence of the AE/SAE onset relative to administration of the investigational product is reasonable, but the AE/SAE could have been due to another equally likely cause.
Probable:	There is evidence of exposure to the investigational product, the temporal sequence of the AE/SAE onset relative to administration of the investigational product is reasonable, and the AE/SAE is more likely explained by the investigational product than by any other cause.
Definite	There is evidence of exposure to the investigational product, the temporal sequence of the AE/SAE onset relative to administration of the investigational product is reasonable, the AE/SAE is more likely explained by the investigational product than by any other cause, and the AE/SAE shows a pattern consistent with previous knowledge of the investigational product or investigational product class.

11.2.8.3.4. Outcomes and Actions Taken

All unresolved AEs will be followed for a minimum of 7 days (unless the AE is an ongoing pregnancy which must be followed to conclusion) after the subject's final study visit, unless the investigator's judgment dictates otherwise, the event has resolved or stabilized prior to the 7-day period, or the subject is lost to follow-up.

Investigators are not obligated to actively seek AEs or SAEs in former study subjects that occur following the follow-up period.

For each recorded AE or SAE, the investigator must make an assessment of outcome at the time of last observation, as follows:

Fatal:	The subject died
Resolved without Sequelae:	The AE or SAE has ended
Resolved with Sequelae:	The AE or SAE has ended but changes are noted from baseline
Unresolved – Ongoing:	The AE has not ended and is ongoing at the end of the reporting period (i.e., 7 days after the final Follow-up visit) and the investigator deems that further follow up is not medically required
Unknown – Lost to Follow-up:	Lost to follow-up after repeated unsuccessful attempts to contact the subject

Actions taken with respect to investigational agents (discontinuation or not) will also be recorded. In addition, if the AE was treated (medications or other physical measures), this will also be recorded.

11.2.8.4. Reporting Serious Adverse Events

11.2.8.4.1. 24 hour Reporting Requirements (Initial Report)

Any SAE, including death due to any cause, which occurs to any subject from the time of signing consent through the final follow-up visit whether or not related to the investigational product, must be reported within 24 hours of knowledge of the event by completing the AE/SAE eCRF. This will trigger an automatic notification of the SAE via an email communication to the sponsor and Fast-Track. Fast-Track will notify the medical monitor upon receipt of the notification and coordinate communications with the medical monitor.

11.2.8.4.2. 3-Day Supporting Documentation Requirements (Follow-up Report)

Additional written documentation for all SAEs must be received by the medical monitor within 3 days of reporting the event. Required eCRF that must be completed include the following:

- AE/SAE eCRF (revised if additional information is available)
- Concomitant Medication eCRF

In addition, paper copies of the following may be requested

- Copies of source documents pertinent to the event (laboratory reports, medical chart notes, etc.). These should be identified only by Subject number and not include any subject identification information prohibited by Health Insurance Portability Accountability Act (HIPAA).
- Any other relevant information necessary to support the investigator's judgment regarding the SAE's relatedness severity to the investigational product OR by request of the medical monitor.

These paper documents may be submitted by facsimile, as email attachments, or by attaching them to the subject's eCRF casebook.

Care should be taken by the Investigator to record any medication taken by the subject for treatment of the event, and if hospitalized to report all medication taken during hospitalization. Also, if hospitalized, all associated adverse experiences that occur during hospitalization should be reported on the eCRF.

The sponsor will report in an IND safety report any suspected adverse reaction that is both serious and unexpected.

12. STATISTICS

A formal statistical analysis plan (SAP) will be finalized prior to locking the database and commencing with the analysis. Any changes to the SAP will be outlined in the final study report. The SAP will provide additional details on the planned analyses including shells for tables, listings, and figures.

12.1. Analysis Populations

The intention-to-treat (ITT) population will consist of all subjects who are enrolled into the study and received any amount of investigational product.

The per-protocol (PP) population will consist of all subjects in the ITT population who received all five (5) TdaP vaccinations and completed the 6 month follow-up visit after the final vaccination.

12.2. Description of Statistical Methods

12.2.1. General Approach

For descriptive purposes, dichotomous and categorical variables will be presented as number of observations and percentages; continuous variables will be given as means, standard deviations (SD), median, minimum (min) and maximum (max). As it is expected that titers will not be normally distributed, geometric means (GeoMean) will be used to summarize anti-tetanus and anti-diphtheria antibody titers. SAS version 9.4 will be used to perform the statistical analyses.

12.2.2. Baseline Descriptive Statistics

Demographics, other baseline data, and record of vaccination for all subjects will be summarized in tables.

12.2.3. Safety Analyses

AEs occurring after each vaccination up to the time of the next vaccination and separately over the whole study period will be summarized and presented in listings. Separate tables will be provided for solicited AEs reported within the 3 day period after each vaccination. AEs will be coded using the most recent version of the Medical Dictionary of Regulatory Activities (MedDRA) preferred terms and will be grouped by system, organ, and class (SOC) designation. The severity, frequency, and relationship of AEs to investigational product will be presented by preferred term by SOC grouping. Listings of each individual AE including start date, stop date, severity, relationship, outcome, and duration will be provided. Each AE (based on preferred terminology) will be counted once only for a given study subject within each post vaccination time period prior to the next vaccination or up to the 6-month follow-up visit after the last vaccination. If the same AE occurred on multiple occasions, the highest severity and relationship to investigational product will be assumed within each time period. Likewise an overall summary will be presented by counting each AE one time over the entire study period.

Reactogenicity is defined as the total count of a set of solicited AEs that are expected after a vaccine. A regression analysis will be performed with reactogenicity as the dependent variable and anti-diphtheria titers as the independent variable to determine if there is an association. In addition, 2x2 tables will be created with presence or absence of moderate to severe reactogenicity versus high or not anti-diphtheria titers. Cut points of 75th percentile or 90th percentile of the anti-diphtheria titers will be used to define high level.

Urinalysis results and serum creatinine levels will be presented as summary statistics over time.

The final disposition of all subjects (completed the study or withdrawn early and reason for early withdrawal) will be summarized and provided in a listing. Medications will be presented in a listing.

